Left Atrial imaging prior to Cardioversion: Leveraging computed tomography to rule Out Thrombus. (LA CLOT) – A Pilot Study of Hospitalized and Emergency Department Patients

Principal Investigator: [name]

Co-investigators: [name] [name], [name], [name], [name], [name], [name], [name]

Background

Atrial fibrillation (AF) is the most common cardiac arrhythmia with an estimated 12 million individuals afflicted in European Union, 5.9 million in the USA and 350,000 in Canada are affected.^{1,2} The prevalence of AF is increasing and is projected to rise in the EU to 17.9 by 2050 and 10 million people in the USA by 2060.²⁻⁴ AF and its associated complications are a growing economical burden on the healthcare system and this burden on healthcare will continue to rise.⁵

Atrial Fibrillation Guidelines

Canadian AF guidelines updated recommendations in November 2018 regarding electrical/pharmcologic cardioversion.⁶ Prior to this update, previous guideline recommendations have been:⁷

Non-anticoagulated AF/atrial flutter patients (without indication for emergent cardioversion) requiring rhythm control:

[figure not shown]
- 1) May proceed to cardioversion if non-valvular AF onset was <48hours,
- 2) If AF/atrial flutter onset is unknown or >48 hours
 - a. Anticoagulate and consider cardioversion after 3 weeks
 - b. Admit to hospital for transesophageal echocardiography (TEE) prior to cardioversion
 - c. Refer for outpatient TEE prior to cardioversion

Transesophageal Echocardiography Prior to Cardioversion

TEE is considered the reference standard to rule-out left atrial (LA) and left atrial appendage (LAA) thrombus prior to cardioversion. Several studies have examined the accuracy of TEE for detecting LAA thrombus. Compared to autopsy and intraoperative findings, TEE has a mean sensitivity of 100% and mean specificity of 99%.⁸ Klein et al. showed that TEE could be used prior to cardioversion to exclude LA thrombus with no significant increase in adverse embolic events.⁹

The new Canadian guidelines have made new recommendations (Figure) that may have downstream ramifications on resources.⁶ They have suggested that "pharmacological or electrical cardioversion of symptomatic AF or atrial flutter without at least 3 weeks of previous therapeutic

anticoagulation be reserved for patients with": 1) "non-valvular AF who present with a clear AF onset within 12 hours in the absence of recent stroke or transient ischemic attack (within 6 months)", and 2) "non-valvular AF and a CHADS2 score < 2 who present after 12 hours but within 48 hours of AF onset", and 3) "as an alternative to at least

3 weeks of therapeutic anticoagulation before cardioversion, TEE may be used to exclude cardiac thrombus".

As such, these recommendations will likely reduce the frequency of immediate cardioversions (in the emergency department), increase referrals for inpatient and outpatient TEEs, and increase hospital admissions. We propose a randomized control trial that will assess the utility of cardiac CT to improve patient access and timely care. The results of this study could have worldwide impact by improving patient quality of life and timely access to cardioversion.

Imaging to Rule Out LA Thrombus

Currently, TEE is considered the reference standard technique for the detection of intracardiac thrombus. Although the gold standard, a TEE-guided therapy is still associated with an embolic rate of 0.8%.⁹ TEE does have limitations which include: need for NPO x 6-8 hours, patient discomfort, potential complications associated with the procedure (infection, aspiration, perforation, bleeding, etc) or with sedation.¹⁰

Contrast enhanced ECG-gated cardiac CT (CCT) is a sensitive, noninvasive alternative method used to exclude of left atrial and LAA thrombus. CCT provides high spatial and good temporal resolution and its ability to detect thrombus has been evaluated.¹¹⁻¹⁵ CCT, compared to TEE, for the exclusion of thrombus in the LAA had a sensitivity and specificity of 100% and 99.3%, respectively (Table 1).¹⁶ A high sensitivity is needed to minimize risk of embolus, and if a thrombus is detected on CT, a confirmatory TEE may be performed or patients may receive anticoagulation. Some argue that the potential benefits of CT and its lower associated procedural risk, the risk:benefit ratio would still favour CT.

This research is novel because it will be the first to demonstrate in a RCT, that CT can be used as an alternative to TEE. More importantly, demonstrating that CT is cost-effective would be extremely attractive to all stakeholders given the growing financial burden of healthcare.

Hypothesis

- Primary Hypothesis: Compared to TEE, CCTA will:
 - 1. Reduce time to cardioversion for in-patients
- Secondary Hypotheses: Compared to TEE, CCTA will:
 - 1. Reduce length of hospital or emergency room stay,
 - 2. Improve patient quality of life (QoL),
 - 3. Not increase adverse events (arterial embolism, procedural complications, bleeding),
 - 4. Have superior cost-effectiveness.

Study Objective

Overarching objective: To evaluate CCT as an alternative to TEE to expedite cardioversion, improve patient care and reduce hospital admissions for AF and atrial flutter.

- Primary Objective: To determine if CCT can reduce time to cardioversion for in-patients
- Secondary Objectives:
 - To determine if CCT can reduce length of stay (in-patient hospitalization and emergency department)
 - To determine if CCT improves patient QoL
 - o To determine if CCT is associated with fewer or more adverse events
 - To determine the specificity of CCT (in patients with filling defects and subsequent TEE)

Outcomes Measures

- 1. Time to cardioversion (Time from referral for imaging)
- 2. Hospital admission rate
- 3. Length of hospital stay (in-patient and emergency department stay)

- 4. QoL before cardioversion, at hospital discharge and at 30 days
- 5. Adverse events (embolic (arterial) event, procedural complication, major bleed (need definition))
 - a. Embolic arterial event
 - b. Procedural complication
 - c. All bleeding
 - d. Major bleeding
- 6. Operating characteristics (specificity, PPV) of CCT (subanalysis of patients receiving TEE after CCT)

Study Design

This randomized controlled trial will randomize patients undergoing cardioversion for AF or atrial flutter before 3 weeks of anticoagulation. This pilot (Vanguard) study will aim to demonstrate feasibility of enrolment and assist with final sample size calculation.

Inclusion Criteria

- Patients admitted to hospital or seen in the ED who require LA imaging prior to cardioversion
- Age ≥ 18 years old
- Able and willing to comply with the study procedures

Exclusion Criteria

- Indication for acute cardioversion (e.g. hemodynamic instability, acute coronary syndrome (ACS), or pulmonary edema)
- Unwillingness or inability to provide informed consent
- Contraindication to Cardiac CT
 - Severe renal insufficiency(GFR< 45ml/min)
 - Allergy to intravenous contrast agents
 - Contraindications to radiation exposure (for example, pregnancy)
 - Inability to perform 20-second breath-hold
- Contraindication to TEE
 - Unrepaired tracheoesophageal fistula
 - Esophageal obstruction or stricture
 - Perforated hollow viscus
 - Poor airway control
 - Severe respiratory depression
 - Uncooperative, unsedated patient

Methods

Recruitment

Patients who meet the inclusion/exclusion criteria will be randomized to either the interventional arm (CCT) or standard of care (SOC) arm (TEE). Prior to randomization, written informed consent will be obtained from each patient. Patients will undergo imaging as per clinical routine and reports will be issued immediately.

TEE protocol

TEE will be performed as per clinical routine using multiple standard tomographic planes to rule-out LA/LAA thrombus. Echocardiographic analysis will include: LAA-emptying velocity, and grading the severity of LAA spontaneous ECHO. The severity of the SEC will be graded on a 4 point scale with 1 = minor homogeneous contrast enhancement, 2 = significant homogeneous contrast

enhancement, 3 = significant, dense, and inhomogeneous, slow-moving contrast, and 4 = dense slow-moving contrast.

Cardiac CT protocol

As per local protocol, a non-contrast enhanced prospective ECG-triggered image acquisition will be acquired. This will be followed by a contrast-enhanced prospective ECG-triggered will be acquired using a tri-phasic contrast protocols. Delayed CT images will be acquired 60 seconds after the initial contrast-enhanced CT scan.Cardiac CT image interpretation will be performed as per clinical routine. The LA and LAA will be assess for filling defects and characterized based upon attenuation values. If LA/LAA thrombus cannot be excluded, filling defects will be assessed on the delay images. Increases in attenuation would be consistent with pseudo-thrombus from 'slow flow' and 'incomplete opacification'. Areas where attenuation does not change significantly (persistent filling defect) will be diagnosed as thrombus. It will be recommended that patients with thrombus will undergo TEE.

Prevention of Bias

Enrolled patients will be processed through the usual clinical routine for patient booking and investigators will not influence timing of booking.

Duration of Follow-up

Patients will be followed for 30 days after cardioversion using electronic charts and telephone follow-up for QoL measures.

Sample Size Calculation

This pilot (Vanguard) study will aim to demonstrate feasibility of enrolment and assist with final sample size calculation.

Statistic Methods

Statistical analyses will be performed using SAS and/or SPSS. Statistical significance will be defined as p<0.05. Continuous variables will be presented as means and standard deviations, and categorical variables will be presented as frequencies with percentages. To compare variables, the Wilcoxon rank sum or T-test will be used to compare continuous variables and Fisher's exact test for categorical variables. Costs will be calculated using Ontario Case Costing Initiative and the Ontario Schedule of Physician Fees and Benefits.

Randomization

Randomization will occur at time of referral for TEE and be performed using a random generator. Patients will be stratified according hospital location (CICU versus ward versus emergency department) and according to mode of cardioversion (electrical versus pharmacologic) and patient sex.

Ethical Considerations

The investigator will ensure that this study is conducted in full conformance with the principles of the "Declaration of Helsinki" or with the laws and regulations of the country in which the research is conducted, whichever affords the greater protection to the individual. The study will fully adhere to the principles outlined in "Guideline for Good Clinical Practice" ICH Tripartite Guideline or with local law if it affords greater protection to the patient. It is the responsibility of the investigator, or a person designated by the investigator to obtain signed informed consent from each patient prior to participating in this study after adequate explanation of the aims, methods, anticipated benefits, and potential hazards of the study. The investigator or designee will also explain that the patients are completely free to refuse to enter the study or to withdraw from it at any time, for any reason. If new safety information results in

significant changes in the risk/benefit assessment, the consent form will be reviewed and updated if necessary.

The protocol, informed consent and any accompanying material provided to the patient will be submitted by the investigator to the Ottawa Health Science Network Research Ethics Board (OHSN-REB) as appropriate. An approval letter or certificate (specifying the protocol number and title) from the OHSN-REB must be obtained before study initiation by the investigator specifying the date on which the committee met and granted the approval. This applies whenever subsequent amendments/modifications are made to the protocol. Any modifications made to the protocol, informed consent or material provided to the patient after receipt of the REB approval must also be submitted by the investigator in accordance with local procedures and regulatory requirements.

Conflict of Interest

The investigators have no conflicts of interest to disclose.

Direct Access to Source Data/Documents

The Investigator and the study centre will accept responsibility of monitoring and auditing as well as inspections by the Ottawa Health Science Network Research Ethics Board and the University of Ottawa Heart Institute. They will also provide all study-related records, as well as source documents to these instances when they are requested to. The confidentiality of the participant's identity shall be well protected and consistent with local and national regulations when the source documents are subject to direct access.

Data Handling and Record Keeping

The Investigator will maintain adequate and accurate records to enable the conduct of the study to be fully documented and the study data to be subsequently verified. These documents should be classified into two different separate categories: [1] Investigator's Study File and [2] patient clinical source documents. The Investigator's Study File will contain the protocol/amendments, CRF/DCS and schedule of assessments, Independent Ethics Committee/Institutional Review Board approval with correspondence, sample informed consent, staff curriculum vitae and authorization forms and other appropriate documents/correspondence, etc.

Patient clinical source documents will include patient hospital/clinic records, physician's and nurse's notes, appointment book, original laboratory reports, special assessment reports, signed informed consent forms. All personal health information collected will be kept confidential unless release is required by law. For audit purposes only, the Ottawa Health Science Network Research Ethics Board and the University of Ottawa Heart Institute may review the patients' medical records under the supervision of [name] and his staff. The Master list containing the patients' personal health information will be kept separate from the patient screening and enrollment logs. The Master List which links the patient with the independent study number will only be accessible by [name] and his staff. The master link and study files will be stored separately and securely.

All paper records will be stored in a locked filing cabinet and /or office. All electronic records, including the Master List, will be stored on a secure internal hospital server and password protected, again only accessible by [name] and his staff. No identifiable information will be stored on any mobile devices (laptops, USB keys, CDS, DVDs, etc). The Investigator must keep source documents as described above on file for 10 years after completion or discontinuation of the study. After that period of time the documents may be destroyed, according to local regulations.

Publication Policy

In accordance with standard editorial and ethical practice, the results of this study will be published or presented at congresses or scientific meetings. Patients will not be identifiable in any publications or presentations.

References

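### Secondary hypothesis 3 claims that cardiac CT does not increase adverse events, but the plan offers only a test of difference, with no margin or confidence interval

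*Combined protocol and SAP*

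**What the plan says.** Under Hypothesis, secondary hypothesis 3 states that CCT, compared with TEE, will "Not increase adverse events (arterial embolism, procedural complications, bleeding"). The matching item under Study Objective is neutral: "To determine if CCT is associated with fewer or more adverse events".

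Statistic Methods has one general rule for all categorical outcomes. The test is "Fisher's exact test for categorical variables", the threshold is "Statistical significance will be defined as p<0.05", and for description "categorical variables will be presented as frequencies with percentages". Adverse events are not singled out. No non-inferiority margin, confidence interval, sidedness or criterion for concluding that events were not increased appears anywhere in the document.

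The Background (Imaging to Rule Out LA Thrombus) gives the only event rate for any adverse event class: "a TEE-guided therapy is still associated with an embolic rate of 0.8" per cent. Study Design and Sample Size Calculation give no number of patients. They say: "This pilot (Vanguard) study will aim to demonstrate feasibility of enrolment and assist with final sample size calculation".

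**The concern.** The hypothesis asserts the absence of harm, while the test starts from the assumption of no difference and looks for evidence against it. Failing to find that evidence does not establish the starting assumption, at this or any sample size. The hypothesis and its objective also disagree: one predicts no increase, the other asks which way events go.

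The plan does not say that p≥0.05 will be reported as safe. That reading is an inference. But p<0.05 is the only yardstick the plan provides, so a non-significant result could easily be written up as confirming hypothesis 3.

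Embolism is where this matters most, because it is the main risk of clearing patients for cardioversion by CT instead of TEE. If non-significance is the expected result whether CCT is equal or clearly worse, the p-value tells readers almost nothing. An interval would show how large an increase the data still allow.

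**Working it through.** The plan states no power, event count or margin for adverse events, so there is no figure to reproduce. The question is what Fisher's test could show about embolism.

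**Inputs**
- TEE embolic rate 0.8%: from the Background.
- Significance level 0.05: from Statistic Methods. Sidedness is not stated, so both are shown.
- Patients per arm: not stated. Assumed 50 to 200.
- Allocation: not stated. Assumed 1:1.
- CCT embolic rate 2.4% (3 × 0.8%): an illustrative trebling, not a figure from the plan.

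**Step 1. How many emboli produce p<0.05?** With equal arms and rare events, each embolus falls in either arm with probability close to 1/2.
- Against zero TEE emboli, the two-sided p for k CCT emboli is roughly 2 × (1/2)^k: 0.063 for k = 5 and 0.031 for k = 6. The exact Fisher values at 50 per arm are 0.056 and 0.027. Exact calculation gives a threshold of **6 CCT emboli** (5 one-sided) at 25, 50, 100, 150, 200 and 300 per arm.
- Against one TEE embolus, the threshold is **8** (7 one-sided) from 50 to 300 per arm.

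For comparison, the expected number of CCT emboli after a trebling is 50 × 0.024 = 1.2 at 50 per arm and 100 × 0.024 = 2.4 at 100.

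**Step 2. Chance of flagging the trebling.** Sum Bin(i; n, 0.008) × Bin(j; n, 0.024) over all tables with more CCT emboli (j > i) and Fisher p<0.05:

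| Per arm | Two-sided | One-sided |
|---|---|---|
| 50 | 0.1% | 0.5% |
| 100 | 1.6% | 4.6% |
| 150 | 5.7% | 11.6% |
| 200 | 11.2% | 19.0% |

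For a doubling to 1.6%, the two-sided figures are 0.01%, 0.26%, 1.1% and 2.6%.

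**Step 3. How likely is a table with no emboli?** If both true rates are 0.8%, P(0 vs 0) = 0.992^(2n): 0.992^100 = 45% at 50 per arm, 0.992^200 = 20% at 100, and 0.992^400 = 4% at 200.

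**Step 4. What would intervals show in that case?**
- Exact (Clopper-Pearson) upper 97.5% limit for the CCT rate at zero events = 1 − 0.025^(1/n): 7.1% at 50, 3.6% at 100, 2.4% at 150, 1.8% at 200.
- Newcombe score 95% interval for the difference at 0 vs 0. With equal arms it reduces to ± z²/(n + z²), with z² = 3.84. At 50 per arm this is 3.84/53.84 = ±7.1 points; at 100, 3.84/103.84 = ±3.7 points; at 200, 3.84/203.84 = ±1.9 points.

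Fisher's test returns p = 1 in each of these tables. The intervals show that increases several times the 0.8% base rate remain possible at 50 or 100 per arm.

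**Step 5. Commoner events.** The plan gives no rates for bleeding or procedural complications. For an assumed 10% vs 30%, two-sided Fisher power is 64% at 50 per arm and 93% at 100. The near-silence of the test is therefore specific to rare events. The logical mismatch applies to all of them.

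**The case against.** The strongest reply has four parts.

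1. **The plan never says that p≥0.05 means safe, and Fisher's test is a blanket rule not tied to hypothesis 3.** Both are true. The risk is one of misreading, not an explicit wrong rule. But adverse events are categorical, no other rule covers them, and no wording guards against the misreading.
2. **A two-directional test does suit the neutral objective, and low power for rare events is no fault in a declared feasibility pilot.** Both points stand. The criticism is not that the pilot is too small. It is that a feasibility pilot carries a no-harm hypothesis its analysis cannot address. Adopting the objective's own wording would resolve this.
3. **The size of the problem rests on assumptions.** Sample size, allocation, sidedness and the trebling are all assumed. The 0.8% rate comes with no stated time window, so its fit to the 30-day follow-up cannot be checked. This limits the precision of the figures. The conclusion nevertheless holds from 50 to 200 per arm and for one-sided as well as two-sided testing. It is confined to embolism.
4. **Counts by arm are already planned, so readers could compute intervals themselves.** They could, but pre-specifying the intervals decides what the report will say about safety, and a reader's recalculation does not.

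**Conclusion.** The concern holds. Hypothesis 3 is a no-harm claim with no decision rule that could support it. That conclusion needs no assumption about sample size, because a non-significant test of difference does not show the absence of an increase.

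The size of the practical problem is conditional. With a 0.8% TEE rate, 1:1 allocation and up to 100 patients per arm, the two-sided test would miss a trebling of embolism at least 98% of the time (100% − 1.6% = 98.4% at 100 per arm). At 200 per arm it would still miss it about 89% of the time (100% − 11.2% = 88.8%). For commoner adverse events the test is less weak. The point should be corrected before analysis. It does not threaten the trial's feasibility aim.

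**What to change.** - Reword hypothesis 3 for the pilot as estimation of adverse event rates by arm, in line with the neutral objective.
- For each event class, add to the planned counts and percentages an exact (Clopper-Pearson) 95% interval per arm and a Newcombe score (or exact) 95% interval for the risk difference. The score interval remains usable at 0 vs 0.
- State that p≥0.05 will not be interpreted as no increase.
- Leave any no-harm claim to the main trial, with a margin stated and justified in advance.

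The cost is a few lines of text and two kinds of interval per event class, with no new data or patients. There are two downsides. The pilot will make a less favourable safety statement. And score intervals can disagree with Fisher's test at the edge: with 5 vs 0 events at 50 per arm, Fisher gives two-sided p = 0.056 while the Newcombe interval runs from 0.9 to 21.4 points. The plan should therefore say that the intervals are descriptive.

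### Specificity of CCT cannot be estimated on the pathway the plan describes, because TEE after CCT is recommended only for CT-diagnosed thrombus; PPV is what that pathway can estimate

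*Combined protocol and SAP*

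**What the plan says.** All references are to the combined protocol and SAP.

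- **Study Objective, last secondary objective:** "To determine the specificity of CCT (in patients with filling defects and subsequent TEE").
- **Outcomes Measures, item 6:** "Operating characteristics (specificity, PPV) of CCT (subanalysis of patients receiving TEE after CCT").
- **Recruitment:** patients are "randomized to either the interventional arm (CCT) or standard of care (SOC) arm (TEE"). No patient is assigned both tests.
- **Cardiac CT protocol:** "If LA/LAA thrombus cannot be excluded, filling defects will be assessed on the delay images". Two readings follow. "Increases in attenuation would be consistent with pseudo-thrombus", which makes the scan negative for thrombus. "Areas where attenuation does not change significantly (persistent filling defect) will be diagnosed as thrombus", which makes it positive. Then: "It will be recommended that patients with thrombus will undergo TEE". No TEE is described for resolved defects or for scans with no defect.
- **Imaging to Rule Out LA Thrombus:** TEE is the reference standard, and a CT showing thrombus may lead to either a confirmatory TEE or anticoagulation. Verification is therefore optional even for CT-positives. The same section says that CCT "had a sensitivity and specificity of 100% and 99.3%, respectively (Table 1").
- **Statistic Methods:** no diagnostic-accuracy analysis and no method for partial verification.

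**The concern.** Specificity is the share of thrombus-free patients whom the test calls negative. Its numerator is made up of CT-negatives whom the reference standard has confirmed as thrombus-free. The analysis set is patients with TEE after CCT, and the described route into that set runs through a positive CT. The numerator is therefore empty by design.

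A stated secondary objective and half of outcome 6 would then have no answer. The result might be reported as 0%, or as a figure that mainly reflects who was sent for TEE, and be read beside the 99.3% in Table 1. More patients would not help, and because this is a vanguard pilot, the definition could pass into the larger trial.

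**Working it through.** **1. The plan's own figure.** The mean of the six specificities in Table 1 is (98 + 100 + 98 + 100 + 100 + 100)/6 = 596/6 = 99.33%, which reproduces the stated 99.3%.

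**2. Who is verified in the CCT arm.**

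| CT result | CT call | TEE described | Cells filled |
|---|---|---|---|
| No filling defect | negative | none | none |
| Defect resolves on delayed images | negative | none | none |
| Defect persists | positive | recommended | true positive, false positive |

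The TEE arm has no CCT, so it fills no cell.

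**3. Consequence.** Specificity = TN/(TN + FP), with TN = 0, so it equals 0/(0 + FP). That is 0% if FP ≥ 1 and 0/0 if FP = 0. No assumption about sample size, prevalence or accuracy enters.

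The remaining steps are illustrations. The documents give no sample size, thrombus prevalence or resolved-defect rate, so these are assumed.

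**4. How often it would be undefined.** Assume N = 25 to 100 CCT patients, prevalence p = 5% to 15%, specificity 99.3% (Table 1) and every CT-positive verified. P(no false positive) = 0.993^(N(1 − p)).

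| N | p = 5% | p = 10% | p = 15% |
|---|---|---|---|
| 25 | 84.6% | 85.4% | 86.1% |
| 50 | 71.6% | 72.9% | 74.2% |
| 100 | 51.3% | 53.1% | 55.0% |

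Otherwise the estimate is 0%.

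**5. If resolved defects are meant to count.** Let d be the share of thrombus-free patients with a resolved defect, r the share of those who have TEE, and q the share of false-positive persistent defects that have TEE. Using expected counts, estimated specificity = d·r/(d·r + 0.007·q). With d = 10% (assumed), the true value in the filling-defect subgroup is 0.10/0.107 = 93.5%.

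| r | q | Estimate |
|---|---|---|
| 10% | 100% | 0.010/0.017 = 58.8% |
| 25% | 100% | 0.025/0.032 = 78.1% |
| 50% | 100% | 0.050/0.057 = 87.7% |
| 100% | 100% | 0.100/0.107 = 93.5% |
| 50% | 50% | 0.050/0.0535 = 93.5% |
| 100% | 50% | 0.100/0.1035 = 96.6% |

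The first three rows assume that every CT-positive is verified, which the plan does not require. What matters is r relative to q: the estimate is too low when r < q, right when they are equal and unrelated to true status, and too high when r > q. The subgroup value itself also moves with d: 0.05/0.057 = 87.7% at d = 5% and 0.20/0.207 = 96.6% at d = 20%.

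**6. What PPV would look like.** With sensitivity 100% (Table 1), expected CT-positives = N·p + 0.007·N·(1 − p). This gives 1.4 to 3.9 of 25, 2.8 to 7.8 of 50, and 5.7 to 15.6 of 100.

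Take N = 100 and p = 10%: 10 true positives and 0.63 expected false positives, rounded to 1, so 11 CT-positives and 89 CT-negatives. Suppose TEE confirms 7, refutes 1 and is not done in 3:

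- Verified PPV is 7/8 = 87.5% (Clopper-Pearson 95% CI 47.3% to 99.7%).
- Bounds are 7/11 = 63.6% if the 3 are all false and 10/11 = 90.9% if all true.
- Whole-arm specificity, taking CT-negatives as thrombus-free, is 89/90 = 98.9% if the 3 are all true and 89/93 = 95.7% if all false.

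**The case against.** The strongest reply is that the objective speaks of filling defects, not thrombus. The Cardiac CT protocol uses that term for early defects, some of which resolve, and outcome 6 takes in anyone who has TEE after CCT. Imaging follows clinical routine, so a patient with a resolved defect could be sent for TEE. This stands to the extent that zero verified negatives describes the planned pathway and does not predict that none will ever occur. It does not rescue the objective, because no TEE is planned for those patients and nothing fixes who among them would be verified.

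Three stronger conclusions that a reader might draw are not supported:

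- *Only TEE in every patient with a resolved defect would give a valid figure.* That is neither necessary nor sufficient. Equal 50% verification in both groups, unrelated to true status, also gives 93.5%, whereas full TEE of resolved defects with half of the false positives verified gives 96.6%. Known sampling fractions with weighting would also be valid.
- *Referral-driven estimates must be too low.* That holds only if persistent defects are verified at the higher rate.
- *A filling-defect specificity is not comparable with the 99.3%.* Table 1 does not describe its populations, so comparability cannot be established either way.

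It may also be said that CT-negatives can be presumed thrombus-free. The plan does not state this, and the restriction to patients with TEE excludes it.

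Finally, this is a feasibility pilot, specificity appears in none of the four secondary hypotheses, and PPV is already in outcome 6. All of that is true, and it limits the weight of the point without making the objective answerable.

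**Conclusion.** The point holds for specificity on the described pathway: verified true negatives are zero, so the estimate is 0% or undefined at any sample size. This rests only on the plan's text and the definition of specificity; the percentages in steps 4 to 6 rest on assumed inputs and carry none of the conclusion.

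On the wider reading of filling defects, an estimate may exist. It would be valid for that subgroup only if verification were complete in both groups, were at the same rate in both and unrelated to true status, or followed known sampling fractions with weighting. The plan provides for none of these.

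A reader might infer that outcome 6 fails as a whole. It does not: PPV can be estimated in TEE-verified CT-positives, although optional TEE means that unverified positives must be shown. The primary objective, randomization and safety outcomes are untouched. The point should be fixed, but it does not threaten the trial's main purpose.

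**What to change.** In the secondary objective and in outcome 6, replace specificity with PPV in TEE-verified CT-positives (persistent defect, as the Cardiac CT protocol already defines), with the same analysis set in both places. Report:

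- the exact 95% CI and the false-positive count;
- the number of CT-positives without TEE, with PPV bounds counting them as all true and then as all false;
- patients with resolved defects who had TEE, as descriptive counts only.

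If a specificity figure is kept, report it over the whole CCT arm as CT-negatives / (CT-negatives + TEE-refuted CT-positives). Label it as assuming that CT-negatives are thrombus-free and as high almost by construction, and count unverified positives both ways.

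Cost: no extra procedures. The case report form must record defect status (none, resolved, persistent) and whether TEE followed CCT. Under Ethical Considerations, the amendment goes to the research ethics board. Specificity is given up or becomes assumption-based, and PPV will be imprecise because few patients are likely to be CT-positive.

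### No stated analysis uses the first QoL score, and its timing relative to randomisation is not fixed, so the plan secures no clean baseline for adjusting follow-up QoL

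*Combined protocol and SAP*

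**What the plan says.** The Hypothesis section of the combined protocol and SAP expects CCT, compared with TEE, to improve QoL (secondary hypothesis 2). Outcomes Measures, item 4, gives three assessment times: "QoL before cardioversion, at hospital discharge and at 30 days". No instrument and no main time point are named.

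Statistic Methods has one rule for all comparisons: "the Wilcoxon rank sum or T-test will be used to compare continuous variables and Fisher's exact test for categorical variables". It adds that "Statistical significance will be defined as p<0.05". No covariate, ANCOVA, change score or repeated-measures model appears anywhere, and no sentence is specific to QoL.

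On timing, the Randomization section says "Randomization will occur at time of referral for TEE", and Recruitment says that written consent comes before randomisation. The first QoL score is placed relative to cardioversion and is not related to consent or allocation.

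Sample Size Calculation gives only the purpose: "This pilot (Vanguard) study will aim to demonstrate feasibility of enrolment and assist with final sample size calculation".

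**The concern.** Two gaps meet here.

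First, patients differ in QoL before treatment. A two-sample test of follow-up scores leaves those differences in the error term, although the plan collects a score that might remove part of them.

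Second, that score is not secured as a baseline. Between referral and cardioversion a patient waits and has the allocated test. The primary hypothesis is that the wait differs by arm. The section on imaging to rule out thrombus lists fasting, discomfort and sedation risk among the limitations of TEE. A questionnaire completed during that interval could already reflect the arm, and adjusting for it could then bias the QoL comparison.

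At stake are the precision of the QoL estimate and, if the first score is later used as a baseline, its validity. Precision can still be recovered at analysis if a true baseline exists. The time at which the questionnaire was given cannot be corrected once patients are enrolled.

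**Working it through.** **Inputs.** The documents give alpha 0.05 but no sidedness, pilot size, allocation ratio, QoL SD, effect size or correlation, so there is no stated figure to reproduce. Assumed: two-sided test, 1:1 allocation, a true difference of 0.5 SD, 25 or 50 per arm, and a within-arm correlation ρ between first and follow-up score of 0.3, 0.5 or 0.7.

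**Step 1: precision, given a score taken before randomisation.** Variance of the ANCOVA estimate relative to the unadjusted one is 1 − ρ².

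| ρ | 1 − ρ² | Excess variance of plain test, 1/(1 − ρ²) − 1 |
|---|---|---|
| 0.3 | 0.91 | 10% |
| 0.5 | 0.75 | 33% |
| 0.7 | 0.51 | 96% |

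A simulation at ρ = 0.5 (4000 runs, 63 per arm) gave a variance ratio of 0.748, against 0.75 in theory.

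**Step 2: power.** Noncentral t with noncentrality [0.5/√(1 − ρ²)] × √(n/2), on 2n − 2 degrees of freedom for the plain test and 2n − 3 with the covariate. Example at n = 50 and ρ = 0.5: (0.5/0.866) × √25 = 2.89, against 0.5 × √25 = 2.50 unadjusted.

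| n per arm | Unadjusted | ρ = 0.3 | ρ = 0.5 | ρ = 0.7 |
|---|---|---|---|---|
| 25 | 41% | 44% | 52% | 68% |
| 50 | 70% | 74% | 82% | 93% |

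**Step 3: a change score is not an equivalent remedy.** Its variance ratio is 2(1 − ρ): 1.4, 1.0 and 0.6 at the three correlations. It is less precise than ignoring the first score when ρ is below 0.5.

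**Step 4: what happens if the first score is taken after allocation.** Suppose the arms already differ by g SD on that score because of the wait or the test, and the total effect on follow-up QoL is d. ANCOVA then estimates d − ρg. With g = 0.2 in favour of CCT, the shift is −0.06, −0.10 or −0.14 SD at ρ = 0.3, 0.5 or 0.7. In simulation at ρ = 0.5, a true 0.50 was estimated as 0.40 by ANCOVA, while the plain comparison stayed at 0.50. A change score shifts by the whole of g, that is by −0.2 SD. The value of g is also an assumption. If g has the opposite sign, the bias reverses.

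The gains in steps 1 and 2 therefore belong only to a score taken before randomisation. For a score taken later, leaving it out is the safer analysis.

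**The case against.** The strongest reply is that the plan makes no wrong choice about QoL. The Statistic Methods rule is generic: it names neither QoL nor 30 days, and it does not exclude a two-sample test on change scores. That stands. A reader might infer that the plan commits to an unadjusted test of 30-day QoL, but the documents do not say so. What they support is that the QoL analysis is unspecified and that the one available rule gives the first score no role.

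A reader might also infer that the first score is collected after randomisation. The text does not establish this. A questionnaire at consent is also before cardioversion, so the wording permits either timing. The defect is that it is left open.

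A third tempting reading is that the pilot will hand an inflated QoL variance to the final trial. No passage says that QoL will size that trial; the primary objective concerns time to cardioversion. A raw SD is also the right input for an unadjusted comparison, and paired pilot scores would let the correlation be calculated later.

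The size of the gain rests wholly on assumed values. At ρ = 0.3 power rises by only 3 to 4 percentage points, and the documents give no reason to expect a higher correlation between a score in AF and one 30 days after cardioversion.

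Finally, moving the questionnaire to consent replaces a listed assessment. If a measure after imaging was intended, to capture the burden of the test or the wait, it would be lost unless kept separately.

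**Conclusion.** The point holds in a limited form. No stated analysis uses the first QoL score, and the plan does not ensure that this score precedes allocation, so as written it cannot be relied on as a covariate. With the score fixed at consent, ANCOVA is a more precise method than the one stated, at almost no cost. The gain runs from small (9% less variance at ρ = 0.3) to large (49% less at ρ = 0.7), and nothing in the documents shows where in that range this trial lies. Effect size, sample size, two-sided testing and 1:1 allocation are likewise assumptions.

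The consequence is modest. QoL is secondary, the study is a feasibility pilot, and no power is claimed for any endpoint. The change is worth making before enrolment, mainly because the timing of the questionnaire cannot be repaired afterwards.

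**What to change.** - **Outcomes Measures, item 4:** take the first QoL questionnaire at consent, before allocation. If a measure after imaging and before cardioversion is wanted, keep it as an additional outcome and do not use it as a baseline.
- **Statistic Methods:** compare discharge and 30-day QoL by ANCOVA (follow-up score on arm plus pre-randomisation score), and report the adjusted mean difference with its 95% confidence interval. State that a first score taken after randomisation will not be adjusted for as a baseline.
- **Reporting:** give the pilot's QoL SD and the correlation between baseline and follow-up, in case QoL is used in planning the final trial.

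**Cost.** A few sentences and no extra patients. The number of questionnaires is unchanged if the consent questionnaire replaces the one before cardioversion, and rises by one per patient if both are kept. Consent already precedes randomisation, so no new contact is needed.
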